## ***Follow Up***

Patients with HCC usually require either CT scan or MRI of the abdomen to be performed routinely every three months to monitor tumor progression. Patients undergoing any locoregional treatment usually require a CT scan or MRI of the abdomen to be performed 4-6 weeks after the treatment and then every three months. Follow up imaging will be the same modality used at baseline (CT or MRI). Patients are usually evaluated in the liver clinic 4 weeks after treatment and then every three months. Subjects receiving proton therapy will also be followed in radiation medicine clinic by their treating radiation oncologist every 3 months for the first year then every 6 months. Participants in this study will be followed according to this protocol. No radiological testing will be ordered for the purpose of the study as the recommended assessments follow the current standard of care. Patients will be followed for research purposes until death or transplant, or until which time the study investigators determine the study is complete.

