## ***Methods***

Patients meeting the inclusion and exclusion criteria will be randomized (1:1) by an individual who is not a study investigator using the random number method. Subjects will be registered and randomized by contacting [name] ([name], [[contact]](mailto:[contact])). Subjects will be randomly assigned to one of two groups:

Group 1: patients will receive one or more sessions of TACE (Appendix 3).

Group 2: patients will receive 15 consecutive sessions of proton beam radiation (Appendix 4).

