## ***Secondary Endpoints***

### **1. Time to progression.**

This endpoint reflects the time between randomization and radiological progression as defined by the amendments of the Response Evaluation Criteria in Solid Tumors (RECIST) (16).

**A. Complete Response** is defined as the disappearance of any intratumoral arterial enhancement in all target lesions.

- B. Partial Response** is at least a 30% decrease in the sum of diameters of viable (contrast enhancement in the arterial phase) target lesions, taking as reference the baseline sum of the diameters of target lesions.
- C. Progressive Disease** is an increase of at least 20% in the sum diameters of viable (enhancing) target lesions, taking as reference the smallest sum of the diameters of viable (enhancing) target lesions recorded since the treatment started. Or the appearance of one or more new lesions.

A newly detected hepatic nodule will be classified as HCC- and will be declared as evidence of progression- when its longest diameter is at least 10 mm and the nodule shows the typical vascular pattern of HCC on dynamic imaging. Lesions larger than 10 mm that do not show a typical vascular pattern can be diagnosed as HCC by evidence of at least 1 cm interval growth in subsequent scans.

- D. Stable Disease** is any cases that do not qualify for either partial response or progression disease.

MRI or CT-scan of the abdomen will be used to determine the targeted lesions for treatment and its baseline measurements. Target lesions will be measured using a single linear summation of the large diameter of the tumor. The average of two measurements by two independent radiologists will be considered for baseline and follow up assessment.

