## **2. Downstaging**

This endpoint will be applied to subjects in whom their tumor burden exceed Milan criteria but meet San Francisco criteria (Appendix 1). The direct measurement of the longest diameter of the viable tumor will be compared pre-and-post treatment. Usually, patients with San Francisco criteria will not be qualified for MELD score exception upgrade on UNOS waiting list unless their tumor burden is down-staged to Milan criteria using one of the locoregional treatments. Measuring this endpoint will help in comparing the efficacy of proton versus TACE in downstaging tumor in patients who meet San Francisco criteria.

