## **Data and Statistics**

Data will be evaluated according to intent to treat analysis. One- and two-year survival will be compared between two groups using competing risk analysis. This analysis will provide an estimate of HCC-related death in the presence of alternate yet plausible outcomes such as death from liver failure or liver transplantation. It is also a better technique in illustrating differential rates of competing outcomes in patients waiting for liver transplantation. This analysis will limit the effects of confounding factors such as death from liver disease. Secondary end points will be compared using Student's *t*-test for quantitative data and chi-squared ( $\chi^2$ ) test or Fisher's exact test for qualitative data. Demographics and standard of care laboratory data between groups will be compared. Logistic regression will be used to determine independent factors affecting survival.

The study is designed and powered to show at least 15% difference in mortality between two groups. Group size is calculated by assuming that patients in the TACE group will have at least 15% improvement in 2-year survival compared to the proton beam group. With 110 patients in each group the study has 80% power to detect a 15% difference in the mortality between two groups. We are not expecting any significant drop out because both treatments are considered crucial for patients' survival; and also based on our experience in treating these patients for many years at LLUMC. The level of significance is 0.05 (2-sided) for all statistical tests. The Statistical Package for the Social Sciences (SPSS 16.0 for window; SPSS, Inc., Chicago, Illinois) was used for all statistical analyses.

We will conduct an interim analysis after randomizing 40 patients in each group. This analysis will determine if there is any early significant difference in survival between two groups. The interim report will be submitted to the Institutional Review Board.

Data will be collected anonymously and subjects will be identified using a numerical code. The code will be stored at the PI and Co-PI office. The study database will be maintained and stored in the department of radiation medicine. Only PI, CO-PI and research coordinators will have access to the data.

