### **Transarterial Chemoembolization Treatment Protocol**

This procedure is done with the help of fluoroscopy (type of x-ray) imaging. A catheter (long, narrow tube) is inserted into the femoral artery in the groin and is threaded into the aorta (the main artery of the body). From the aorta, the catheter is advanced into the hepatic artery. Once the branches of the hepatic artery that feed the liver cancer are identified, the chemotherapy is infused and the arterial branch that supply the tumor is embolized using Gel Foam or Lipoid. The whole procedure takes one to two hours, and then the catheter is removed.

The patient generally stays in the hospital overnight for observation. A sandbag is placed over the groin to compress the area where the catheter was inserted into the femoral artery. The nurses periodically check for signs of bleeding from the femoral artery puncture. They also check for the pulse in the foot on the side of the catheter insertion to be sure that the femoral artery is not blocked as a result of the procedure. (Blockage would be signaled by the absence of a pulse).

Generally, the liver tests increase (get worse) during the two to three days after the procedure. This worsening of the liver tests is actually due to death of the tumor (and some non-tumor) cells. The patient may experience some post-procedure abdominal pain and low-grade fever. However, severe abdominal pain and vomiting suggest that a more serious complication has developed. Imaging studies of the liver are repeated in six to 12 weeks to assess the size of the tumor in response to the treatment.

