#### Proton Dose to CTV

All doses will be prescribed to a point at or near the center of the CTV target region. The total dose delivered will be 70.2 CGE given in 15 fractions over a three-week course. The uniformity of dose across the target region will not vary by more than 10% of the prescribed dose. At least two beams will be treated each day to reduce the dose at the beam entry site.

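### The first TACE response scan has two conflicting times and downstaging has no named scan; unequal scan timing shifts time to progression only slightly (minor)

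*Combined protocol and SAP*

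**What the plan says.** Under Secondary Endpoints, time to progression starts at randomization: "This endpoint reflects the time between randomization and radiological progression". Follow Up dates imaging from treatment instead, with CT or MRI "to be performed 4-6 weeks after the treatment and then every three months", and says that trial participants will be followed in this way. It adds that "No radiological testing will be ordered for the purpose of the study".

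The two treatments differ in length. Appendix 4 has the proton dose "given in 15 fractions over a three-week course". Methods allows any number of TACE sessions from one upward, and Appendix 3 gives one to two hours for the procedure. Nothing says which session starts the scan clock.

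Appendix 3 then gives its own timing for TACE: "Imaging studies of the liver are repeated in six to 12 weeks to assess the size of the tumor in response to the treatment". For downstaging, the "longest diameter of the viable tumor will be compared pre-and-post treatment", with no week or visit attached to the second measurement.

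Data and Statistics gives the analysis: "Secondary end points will be compared using" Student's t-test for quantitative data and a chi-squared or Fisher's exact test for qualitative data. It names no curve, log-rank test or hazard ratio for progression.

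**The concern.** Two separate matters are at stake.

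The first is downstaging. Viable tumor diameter changes with time after treatment, so a fair comparison measures both arms at the same interval. The protocol gives two intervals for TACE and does not say which measurement counts. Staff who follow the text for each arm could measure TACE later than proton. If the scan is chosen once results are known, the choice is open to selection.

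The second is time to progression. Progression is dated at the scan that detects it. If one arm is scanned systematically earlier relative to randomization, its progressions are dated earlier even when the disease behaves identically. A curve or hazard ratio would pick up that difference in timing as if it were a treatment effect.

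**Working it through.** The plan has no figure of its own to reproduce here. It gives no assumed progression rate, no number or spacing of TACE sessions, and no delay from randomization to treatment. Steps 1 and 2 use the document's own times, except for one marked assumption. Steps 3 to 5 rest on assumed values.

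**1. Downstaging scan.** The midpoint of the Follow Up window is (4 + 6)/2 = 5 weeks, and that of the Appendix 3 window is (6 + 12)/2 = 9 weeks. Under the mixed reading (Appendix 3 for TACE, Follow Up for proton) the TACE scan is on average 9 − 5 = 4 weeks later after treatment. If Follow Up governs both arms, the gap is zero.

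**2. First scan counted from randomization, treatment starting at once.**
- Proton: 3 + 4 = 7 to 3 + 6 = 9 weeks.
- Single-session TACE: 4 to 6 weeks, so 3 weeks earlier than proton.
- Two TACE sessions six weeks apart, clock from the last (assumed): 6 + 4 = 10 to 6 + 6 = 12 weeks, so 3 weeks later than proton.

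**3. Effect on a hazard ratio when there is no true difference.** Simulation with 110 patients per arm (Data and Statistics), the same exponential progression in both arms, and the first scan uniform in its window, then every 13 weeks. Progression is dated at the first scan on or after the true time, with censoring at week 104; 3,000 trials per case. The hazard ratio is the one-step estimate exp[(O − E)/V] from the log-rank test. Entries are proton/TACE hazard ratio and log-rank false-positive rate (nominal 5%).

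| Case (assumed) | Median 26 wk | 39 wk | 52 wk |
|---|---|---|---|
| Single session, exact timing | 0.92, 10% | 0.95, 6% | 0.97, 5% |
| Two sessions, exact timing | 1.09, 10% | 1.05, 6% | 1.03, 5% |
| Single, 0-4 wk start delay, repeat scans ±2 wk | 0.95, 7% | 0.97, 6% | 0.98, 5% |
| Two, same scatter | 1.09, 9% | 1.06, 7% | 1.05, 6% |
| 25% have two sessions, exact timing | 0.96, 6% | 0.98, 6% | 0.99, 5% |
| TACE at Appendix 3 window, exact timing | 1.04, 6% | 1.02, 5% | 1.01, 6% |

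With half the TACE arm having two sessions, the hazard ratio is 1.00 to 1.01. With a 0-8 week start delay and ±3 weeks on repeat scans, it is 0.98-0.99 (single) and 1.02-1.03 (two), with 5-6% false positives. Giving both arms the proton schedule returns 1.00 and 4-6%, as it should.

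The shape of the progression hazard matters somewhat. For single-session TACE at a 26-week median, a Weibull shape of 1.5 gives 0.87 and 17% with exact timing, or 0.92 and 9% with the smaller scatter. A shape of 0.75 gives 0.94 and 8%, or 0.95 and 6%.

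**4. The planned t-test.** Applied to progression times observed by week 104, it rejects 4-6% of the time in every exponential case above. Its weakness is power, because it leaves out patients who have not progressed. At an assumed true hazard ratio of 0.65, with single-session timing and medians of 26 to 52 weeks, it had 17-40% power against 78-93% for a log-rank test. Part of the log-rank figure comes from the timing shift, which favors proton in that case. The size of the gap is what matters here, not the exact values.

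**5. Does interval censoring remove the shift?** With each progression placed between the last progression-free scan and the first scan showing it, an exponential interval-censored model gives hazard ratios of 0.99-1.01 and 4-6% false positives in the exponential cases. If the true shape is 1.5, a constant-hazard model stays unbiased but rejects only 0.5-2%. A Weibull interval-censored model gives 0.99-1.01 and 3-6% under shapes 1.0 and 1.5. The baseline should therefore be flexible.

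**The case against.** The best defense is that Follow Up governs. It states one rule for any locoregional treatment and applies it to participants, whereas Appendix 3 reads as a general account of the procedure. On that reading both arms are scanned 4-6 weeks after treatment and the 9-against-5-week contrast disappears. This is a reasonable reading, but Appendix 3 is headed as the TACE treatment protocol, Methods refers to it for the TACE arm, and no text ranks the two. The conflict stands, though the 4-week gap is conditional.

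Second, the planned analysis is a t-test, whose false-positive rate does not move, so the hazard ratios above measure an analysis the plan does not name. That is correct and limits the point to minor. Dropping the t-test rests on its handling of censoring and its low power, not on the scan offset.

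Third, every driver of the offset's size is assumed. This also stands. A reader might infer that the offset biases time to progression strongly, or in a known direction. The documents do not support that. The direction reverses between one and two sessions, and a mix of the two nearly cancels. Effects as large as 0.85 with 22% false positives (single session) or 1.21 with 28% (two) need a median of about 13 weeks. The protocol gives no median; its background section reports only local control of 75-96% after proton.

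**Conclusion.** The concern holds as a minor one. The protocol contradicts itself on the TACE response scan and leaves the downstaging scan unnamed. If each arm follows its own text, the average gap is about 4 weeks (9 against 5).

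The mismatch between randomization-based progression times and treatment-based scans is real but small. A hazard ratio would shift to about 0.92-1.09 at assumed exponential medians of 26 to 52 weeks, and less with realistic scatter or mixed session numbers. A rising hazard with exact timing could push it to 0.87. These figures depend on assumed medians, delays, session counts and spacing.

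A reader might also infer that the trial's main conclusion is at risk, or that scans must be fixed to calendar weeks from randomization. Neither follows. Overall survival needs no scan, and an interval-censored analysis removes the shift without re-timing any scan.

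**What to change.** 1. In Appendix 3, replace the imaging sentence with a reference to Follow Up. In Downstaging, name the scan 4-6 weeks after treatment ends as the post-treatment measurement in both arms. Because Methods sets no limit on TACE sessions, a clause saying which session counts as the end of treatment would help; this is missing detail, not a further fault.
2. In Data and Statistics, replace the t-test for time to progression with an interval-censored time-to-event method with a flexible baseline. Use actual scan dates: the last progression-free scan and the first scan showing progression. State its assumption that scan timing depends only on earlier observed findings. If repeat TACE is prompted by residual tumor that the scans did not record, that assumption could fail.

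The cost is a few sentences and one analysis. Data and Statistics names SPSS 16.0; whether it offers an interval-censored routine was not checked, so another package may be needed. No scan is added, so the bar on study-only imaging is respected.

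Fixing later scans at common weeks from randomization can be left out or kept optional. It would re-time routine care, and item 2 already deals with the shift.

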## **Data and Statistics**

Data will be evaluated according to intent to treat analysis. One- and two-year survival will be compared between two groups using competing risk analysis. This analysis will provide an estimate of HCC-related death in the presence of alternate yet plausible outcomes such as death from liver failure or liver transplantation. It is also a better technique in illustrating differential rates of competing outcomes in patients waiting for liver transplantation. This analysis will limit the effects of confounding factors such as death from liver disease. Secondary end points will be compared using Student's *t*-test for quantitative data and chi-squared ( $\chi^2$ ) test or Fisher's exact test for qualitative data. Demographics and standard of care laboratory data between groups will be compared. Logistic regression will be used to determine independent factors affecting survival.

The study is designed and powered to show at least 15% difference in mortality between two groups. Group size is calculated by assuming that patients in the TACE group will have at least 15% improvement in 2-year survival compared to the proton beam group. With 110 patients in each group the study has 80% power to detect a 15% difference in the mortality between two groups. We are not expecting any significant drop out because both treatments are considered crucial for patients' survival; and also based on our experience in treating these patients for many years at LLUMC. The level of significance is 0.05 (2-sided) for all statistical tests. The Statistical Package for the Social Sciences (SPSS 16.0 for window; SPSS, Inc., Chicago, Illinois) was used for all statistical analyses.

We will conduct an interim analysis after randomizing 40 patients in each group. This analysis will determine if there is any early significant difference in survival between two groups. The interim report will be submitted to the Institutional Review Board.

Data will be collected anonymously and subjects will be identified using a numerical code. The code will be stored at the PI and Co-PI office. The study database will be maintained and stored in the department of radiation medicine. Only PI, CO-PI and research coordinators will have access to the data.

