## **Transarterial Chemoembolization (TACE)**

Multiple studies have shown contradictory results regarding the efficacy of TACE in improving survival compared to other treatments. The majority of these studies are retrospective studies or used a small sample of patients. These contradictory results have been attributed to the difference in endpoints of these studies and the multiple variables such as tumor size and liver function that usually impact and confound the outcome.

In one large study involving several institutions in Italy, chemoembolization did not improve survival compared to supportive care only. Patients who did not undergo TACE lived as long as patients who received TACE, even though the tumors were more likely to shrink in size in patients who were treated (8). Llovet et al. used TACE as a palliative treatment in a prospective, randomized controlled trial published in 2002 on 112 patients with intermediate stage HCC not felt to be candidates for other therapies. The patients randomized to TACE versus supportive care only. A significant increase in survival for the chemoembolization group was observed when compared with control (82% and 63%, 1-and 2-year survival, respectively, compared with 63% and 27%) (9). A study in Japan has shown that TACE can downstage liver cancer (10). Downstaging created the option for transplant in some of these patients. Otherwise, these patients had tumors that were not operable (eligible for operation) or not qualified for liver transplantation because of the initial large size of their tumors (10). More importantly, this study showed an improvement in survival in patients whose tumors became considerably smaller. In the U.S., trials are underway to see whether doing TACE before liver transplantation increases patient survival as compared to liver transplantation without TACE. Risk and common side effects of TACE include: bleeding, infection, worsening liver function, perforation of the common bile duct, veins or arteries, abdominal pain, nausea, vomiting, and fever.

It is reasonable to conclude that TACE is a procedure with acceptable side effects and a controversial small advantage in improving survival, especially in patients with small tumor and for patients waiting for liver transplantation. TACE can be used only in patients with relatively preserved liver function. The reason for this is that these procedures, as mentioned previously, can lead to liver failure in individuals with poor liver function.

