## ***Primary Endpoint***

The primary end point of the study is to measure ***overall survival*** defined as the time from randomization until death. In order to control for non-cancer death related factors that may compound the survival rate, a competing risk analysis rather than Kaplan-Meier will be used to compare the survival between the two groups.

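### Survival is to be compared at both one and two years, each at two-sided 0.05, and the plan does not say which comparison decides the trial

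*Combined protocol and SAP*

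**What the plan says.** Four statements in the combined protocol and SAP bear on this.

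- **Primary Endpoint.** Overall survival is "defined as the time from randomization until death", with no fixed time point. The method is that "a competing risk analysis rather than Kaplan-Meier will be used to compare the survival between the two groups". No specific test is named.
- **Data and Statistics, analysis.** "One- and two-year survival will be compared between two groups using competing risk analysis". The two time points appear side by side with no ranking.
- **Data and Statistics, significance level.** "The level of significance is 0.05 (2-sided) for all statistical tests". No adjustment or hierarchy follows.
- **Data and Statistics, sample size.** "Group size is calculated by assuming that patients in the TACE group will have at least 15% improvement in 2-year survival", and "With 110 patients in each group the study has 80% power to detect a 15% difference in the mortality between two groups". Sizing therefore uses 2 years, but the section does not say that the 2-year comparison is the primary test.

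**The concern.** The primary outcome could be tested in at least three ways: at 1 year, at 2 years, or over the whole follow-up. The plan names two of these explicitly, leaves room for the third, and gives each the full 0.05. Nothing in the text stops a report from calling the trial positive on a significant 1-year difference with a null 2-year difference, or the reverse. The choice could be made after the results are known.

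If either time point may carry the claim, the two-sided 5% level no longer describes the chance of a false positive primary conclusion.

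**Working it through.** **The plan's own figures.** The plan states 0.05 per test and no overall false-positive rate, so there is no overall rate to reproduce. The 110 per group with 80% power cannot be checked directly either, because no base survival rate is given. That is a separate matter and is not needed here.

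**Inputs.**
- Two comparisons, each at two-sided 0.05 (critical value 1.96), from Data and Statistics.
- Equal allocation: patients "will be randomized (1:1) by an individual who is not a study investigator" (Methods).
- Survival rates: *assumed*. The only pairs of 1- and 2-year rates in the documents are those of the cited randomised trial of TACE against supportive care: "82% and 63%, 1-and 2-year survival, respectively, compared with 63% and 27" (both in per cent; section on Transarterial Chemoembolization).
- All-cause survival with no censoring before 2 years: *assumed*.

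**Step 1: correlation of the two tests when the arms do not differ.** Let S1 and S2 be survival at 1 and 2 years, F = 1 − S, and n the number per arm. Without censoring, each estimate has variance S·F/n and their covariance is F1·S2/n. Hence

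rho = sqrt[(F1/S1) / (F2/S2)].

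- TACE-arm rates, 82% and 63%: F1/S1 = 0.18/0.82 = 0.2195; F2/S2 = 0.37/0.63 = 0.5873; rho = sqrt(0.2195/0.5873) = 0.61.
- Control-arm rates, 63% and 27%: F1/S1 = 0.37/0.63 = 0.5873; F2/S2 = 0.73/0.27 = 2.7037; rho = sqrt(0.5873/2.7037) = 0.47.

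**Step 2: chance of at least one false positive.** This is 1 − P(|Z1| < 1.96 and |Z2| < 1.96) for a bivariate normal with correlation rho. With independence it is 1 − 0.95² = 0.0975.

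| Case | rho | At least one false positive |
|---|---|---|
| Independent tests (upper case) | 0 | 9.75% |
| Survival 63% and 27% | 0.47 | 9.2% |
| Survival 82% and 63% | 0.61 | 8.7% |
| Higher correlation | 0.8 | 7.8% |
| Higher correlation | 0.9 | 7.0% |
| One test decides | – | 5% |

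A simulation with 110 per arm and 400,000 runs gave 9.1% for the 63%/27% pair and 8.8% for the 82%/63% pair, in line with the formula.

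**Step 3: how far the lower end reaches.** The rate falls towards 5% as rho approaches 1, so 7.0% is not a strict floor. But rho = 0.9 needs very few deaths in the second year. With S1 = 0.82, F2/S2 = 0.2195/0.81 = 0.271, so S2 = 1/1.271 = 0.787, a fall of about 3 percentage points from year 1 to year 2.

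**Step 4: letting both time points decide.** Bonferroni at 0.025 each holds the total at or below 5%. With illustrative 2-year rates of 63% and 48%, power at 110 per group falls from 61% to 50%, and 80% power needs 208 per group instead of 172.

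**The case against.** The strongest reply is that the plan has one primary endpoint and, read naturally, one test. The Primary Endpoint section describes a single time-to-event outcome and a single competing-risk comparison. The 1- and 2-year figures could simply be points at which that one result is reported. The sample size uses 2 years, and no sizing refers to 1 year. On either reading the rate for this comparison is 5%.

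Much of this stands. A reader might infer that the trial has an 8.7% false-positive rate as a fact of its design. The documents do not support that, because no sentence says that either time point suffices for success. A reader might also infer that the plan gives 2 years no special standing; the sizing statement contradicts this.

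The numerical inputs are also open to challenge. The rates come from a different trial, against supportive care. The calculation treats all-cause survival without censoring before 2 years. Data and Statistics instead describes an estimate of HCC-related death, with liver-failure death and transplantation as competing outcomes, and Follow Up ends at death, transplant or study completion. The correlation for the planned analysis is therefore unknown, and a single precise figure would claim too much.

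The reply does not remove the gap. A sizing assumption is not a decision rule, the Primary Endpoint section names no test, and the sentence that describes the survival comparison gives both time points equal standing.

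The interim look, which also has no stated boundary, is a separate issue. It is not part of these figures and adds no weight to this point.

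**Conclusion.** The point holds as an ambiguity in the primary analysis. The plan allows two comparisons of the primary outcome at 0.05 each and does not say which decides.

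Its size depends on how the gap is filled. The false-positive rate for this comparison is 5% if one test decides, and roughly 7% to 10% if either time point may support a claim. The second figure assumes all-cause survival, no censoring before 2 years, and a correlation between 0 and 0.9; the plan supplies no rates of its own to narrow it. The two pairs of rates found in the documents give 8.7% and 9.2%.

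This should be corrected, because the choice of decisive test is otherwise open after the data are seen and the correction is cheap.

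**What to change.** Amend Data and Statistics to name exactly one decisive test. Suggested wording:

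> The primary test is the between-group comparison at 2 years after randomization, at a two-sided level of 0.05. One-year survival and any comparison over the whole follow-up are supportive. They will be reported as estimates with confidence intervals and will not be a basis for claiming a difference.

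Two years is the natural choice because the group size already rests on it. The wording should not join a whole-curve comparison and a 2-year comparison as if they were one test, since that would leave the same question open. It should also state the event being compared: Primary Endpoint refers to death, whereas Data and Statistics refers to HCC-related death. Settling which is meant is a separate matter, but the named test needs the answer.

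**Cost.** One short amendment. The sponsor gives up a claim based on 1-year survival alone, and a whole-curve comparison becomes supportive. Sample size and nominal power do not change. If the sponsor wants both time points to be able to decide, alpha must be split, at the cost in power or patients shown in the working.
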